11.3 Relevant protocol deviations

Protocol deviations will have to be documented and should be discussed with the Sponsor.

All protocol deviations will be listed in the study report and reported to the sponsor.

11.4 Statistical analysis plan

A **statistical analysis plan (SAP)** will provide full details of the analyses, the data displays and the algorithms to be used for data derivations. The SAP furthermore will include definitions of major and minor protocol deviations and the link of deviations to the analysis set, which also will be covered in the final study report.

Procedures of reporting any deviations from the original statistical plan (any deviations from the original statistical plan should be described and justified in the protocol and/or in the final report, as appropriate.

The SAP should preferably be a separate document. In the protocol this document should be referenced. Alternatively the SAP could be fully included in the study protocol.

11.5 Missing, unused and spurious data

If less than two blood samples of a patient were taken, the outcome cannot be calculated and therefore, this patient will be excluded from the analysis. The analysis will be carried out per protocol.

If the outcome of a patient can be calculated (more than two blood samples taken) but the patient was withdrawn from the study before week 18, analysis will be carried out 1) by intention to treat analysis, with the duration of treatment as additional covariable and 2) per protocol.

11.6 Endpoints analysis

11.6.1 Primary endpoint analysis

A χ^2 -test will be used for analysis of the primary outcome PNAC.

Additionally, the effect of treatment and other relevant influence factors (i. e. duration of parenteral nutrition, birth weight, amount of enteral feeds in the first week of life) on the primary endpoint will be analyzed using a logistic regression model with stepwise selection

In case of twins, the analysis will be carried out 1) as mentioned above, but only including the firstborn and 2) by calculating a generalized linear model with mother as random factor.

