8.2 Randomization and stratification

On day 0, patients are randomized to one of the two study groups and the study medication is provided. Study subjects will be block randomized (ratio 1:1) and stratified according to sex and birth weight (in two groups: < 750 gram vs. ≥ 750 gram) using an online randomization programme provided by the Center for Medical Statistics, Informatics, and Intelligent Systems of the Medical University of Vienna. In case of twins, randomization will be applied to the firstborn; the twin will be assigned to the other treatment group.

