11.6.2 Secondary endpoint analysis

Bailey Scales of Infant Development III at 12 and 24 months: Differences in the scores of psychomotor development and neurocognitive development, respectively, between the groups will be analyzed by repeated measures ANOVA, also accounting for confounders (e.g. birth weight, IVH Grade 3/4, cystic periventricular leucomalacia, NEC). In case of twins, the analysis will be carried out 1) as mention above, but only including the firstborn and 2) by calculating a mixed model with mother and child as random factor. In case of too many drop outs, descriptive statistics will be carried out.

For Gross Motor function measurements at 12 and 24 months, descriptive statistics will be conducted.

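### The primary chi-square test of PNAC ignores the sex and birth-weight strata used at randomisation; if those strata predict PNAC, the test is mildly conservative and loses a little power

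*Combined protocol and SAP*

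**What the plan says.** **Randomisation.** Section 8.2: "Study subjects will be block randomized (ratio 1:1) and stratified according to sex and birth weight", with weight split at 750 g, which gives four strata. The synopsis agrees. For twins, "randomization will be applied to the firstborn; the twin will be assigned to the other treatment group", so second twins are allocated outside the stratified list.

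**Primary test.** Section 11.6.1: a chi-square "test will be used for analysis of the primary outcome PNAC". The synopsis says the same. Neither place mentions strata, an effect estimate or a confidence interval.

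**Additional model.** The effect of treatment and of "duration of parenteral nutrition, birth weight, amount of enteral feeds in the first week of life" "will be analyzed using a logistic regression model with stepwise selection". The synopsis has necrotising enterocolitis in place of first-week feeds. Sex is in neither list.

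**Twins.** The primary analysis is repeated "only including the firstborn and 2) by calculating a generalized linear model with mother as random factor". Strata are not mentioned.

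**Secondary endpoint.** Section 11.6.2 analyses the developmental scores "also accounting for confounders (e.g. birth weight, IVH Grade 3/4, cystic periventricular leucomalacia, NEC", an open-ended list that includes birth weight and does not name sex.

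**Deferred detail.** Section 11.4 leaves full analysis details to a SAP, which may be a separate document or part of the protocol. Nothing in the text supplied adds the strata. Sex and birth weight are both recorded at birth (sections 8.5.4 and 11.6.4).

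**The concern.** Stratified randomisation makes the arms more alike on the stratification factors than simple randomisation would. If those factors predict the outcome, the difference between arms varies less from trial to trial than the unstratified formula assumes. A test that ignores the strata then uses too large a variance, rejects a true null hypothesis less often than 5%, and gives up some power.

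The additional logistic model does not repair this. Stepwise selection may drop birth weight, and sex is not a candidate. Duration of parenteral nutrition is known only after randomisation, and first-week feeding largely so; a model built on them does not replace a prespecified analysis by stratum.

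At stake is a little power in a trial planned at 80%. There is no added risk of a false positive result.

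**Working it through.** **1. The plan's own figure.** Inputs from section 11.2 and the synopsis: 25% vs 10%, two-sided 0.05, power 80%. With pooled variance and no continuity correction:

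n = [1.96·√(2·0.175·0.825) + 0.8416·√(0.25·0.75 + 0.10·0.90)]² / 0.15² = (1.053 + 0.443)² / 0.0225 ≈ 99.5, so 100 per group.

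The stated 100 is reproduced, and it is the size for an unstratified test. Planned enrolment of 122 per group less the stated 22% leaves 122 × 0.78 ≈ 95 per arm, the number used in steps 2 to 4.

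**2. Size of the unstratified test.** With arms balanced within strata, the ratio of the true to the assumed null variance is

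r = mean of p(1−p) over strata / [p̄(1−p̄)],

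and the actual two-sided size is approximately 2·[1 − Φ(1.96/√r)]. The documents give no PNAC rate by stratum. The rates below are assumptions: two equal weight strata averaging 25%.

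| Rates by stratum | Implied odds ratio | r | Size from formula |
|---|---|---|---|
| 25% / 25% | 1 | 1 | 5.0% |
| 35% / 15% | (0.35/0.65)/(0.15/0.85) ≈ 3 | 0.1775/0.1875 = 0.947 | 4.4% |
| 40% / 10% | (0.40/0.60)/(0.10/0.90) = 6 | 0.165/0.1875 = 0.88 | 3.7% |

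**3. Simulation check.** 400,000 trials per scenario, 48 and 47 infants per stratum per arm. Treated rates for power: 15.2%/4.8% and 17%/3%, each averaging 10%.

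| Control rates | Chi-square null size | CMH null size | Power gain with CMH |
|---|---|---|---|
| 35% / 15% | 4.4% | 5.0% | about 1.1 points |
| 40% / 10% | 3.7% | 4.9–5.0% | about 2.3 points |

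**4. Allowing for loss.** Random loss of 22% from 61 per stratum per arm disturbs the exact balance. At 40%/10% the chi-square null size then moves back towards nominal, to about 4.0%, against about 5% for CMH.

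**5. All four strata, and weaker effects.** 200,000 trials per scenario, 100 per arm, marginal rates held at 25% vs 10%. The share below 750 g was assumed to be 40% or 52%, and the odds ratios are also assumptions.

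| Odds ratios, weight / sex | Chi-square null size | Power change with CMH (points) |
|---|---|---|
| 1 / 1 | 0.049–0.050 | −0.3 |
| 1.5 / 1.2 | 0.048–0.049 | −0.2 to −0.1 |
| 2 / 1.5 | 0.046–0.047 | +0.2 |
| 3 / 1.5 | 0.043 | +0.7 to +0.8 |
| 4 / 2 | 0.038–0.039 | +1.5 to +1.7 |
| 6 / 2 | 0.032–0.034 | +2.1 to +2.6 |

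CMH size stayed at 0.049–0.051 throughout.

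**6. Are the strata prognostic?** Section 11.6.1 counts birth weight among the relevant influences on PNAC, and section 5.1.2 names prematurity as a risk factor. Neither gives a strength. Nothing is said about sex and PNAC.

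**The case against.** The best defence is that the effect is small and conditional. With weight and sex odds ratios up to 2 and 1.5, the chi-square size is 0.046–0.050 and the gain from stratifying is at most about 0.2 points. The 40%/10% case needs an odds ratio of 6. Post-randomisation loss weakens the balance that causes the conservatism, and the error is on the safe side. All of this stands and limits the point to a minor efficiency gain.

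A reader might infer more than the documents support:

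- *That the test is conservative as a fact.* It is so only if the strata predict PNAC. That is implied for birth weight and not stated for sex.
- *That the primary confidence interval is too wide.* Section 11.6.1 specifies no effect estimate or interval, so there is none to be wrong.
- *That sex is excluded from every model.* It is named in none, but the confounder list in section 11.6.2 is open-ended and section 11.4 defers detail to a SAP. Neither supplies strata for the primary test.
- *That stratifying costs nothing.* It loses about 0.1 to 0.3 power points when the strata are weak or not prognostic.
- *That stratifying would make good the power lost through the dropout allowance.* The fall to about 95 evaluable per arm (power about 78%) is a separate matter, and only strongly prognostic strata would offset it.

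**Conclusion.** The point holds in a limited form. The primary analysis does not reflect the stratified randomisation, and no named model guarantees adjustment for either factor. If the strata predict PNAC, the chi-square test is conservative: null size about 4.4% at assumed control rates of 35%/15%, and about 3.7% at 40%/10% (about 4.0% with 22% random loss). The power forgone in those cases is about 1 to 2.5 points, and close to zero for modest stratum effects.

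These sizes rest on assumed stratum rates, equal weight strata and independent infants. Balance within strata is assured by design only for randomised infants, so the reasoning fits the firstborn-only analysis best; no figure is offered for imbalance caused by second twins. Type I error is not inflated and the sample size is not put in doubt. This is a worthwhile, nearly free improvement; it does not challenge the trial's validity.

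**What to change.** In section 11.6.1 and the synopsis, make the primary test a Cochran-Mantel-Haenszel test stratified by sex and birth-weight group (<750 g vs ≥750 g). Report it with the stratified risk difference and its 95% CI, and keep the plain chi-square as supportive. Name this one analysis as primary: a logistic or GEE model estimates an odds ratio, a different effect measure, so the two should not be offered as interchangeable.

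In the twin model with mother as random factor, include sex and birth-weight group as fixed terms that are not subject to stepwise selection. Stratum adjustment handles imbalance introduced by second twins, but dependence within pairs still needs that model.

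Cost: a few sentences of text. Both factors are already recorded at birth and no extra infants are needed. The statistical downside is at most about 0.3 power points if the strata turn out not to be prognostic.

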STATISTICAL METHODOLOGY	
Primary Endpoint PNAC (definition see efficacy endpoint)
 
Null and alternative hypotheses: H₀ : The percentage of PNAC in group 1 (investigational drug) equals group 2 (comparative drug) H₁: The percentage of PNAC in group 1 (investigational drug) does not equal group 2 (comparative drug)
 
Sample size calculation A sample size estimation using a χ^2-test indicated that 200 infants (100/group) are required to detect a 15% difference (10% in group 1 vs. 25% in group 2) with a power of 80% and a two-sided significance level of 0.05. The estimated drop out rate is 22%. Therefore, a sample size of 122 patients per group is planned. For sample size estimation, data were assumed to be independent.
 
Statistical methodology Main analysis set(s) A χ^2-test will be used for analysis of the primary outcome PNAC. Additionally, the effect of treatment and other relevant influence factors (i. e. duration of parenteral nutrition, birth weight, necrotizing enterocolitis) on the primary endpoint will be analyzed using a logistic regression model with

	
stepwise selection. In case of twins, the analysis will be carried out 1) as mentioned above, but only including the firstborn and 2) by calculating a generalized linear model with mother as random factor.
 
Other endpoints
 
Bailey Scales of Infant Development III at 12 and 24 months: Differences in the scores of psychomotor development and neurocognitive development, respectively, between the groups will be analyzed by repeated measures ANOVAs, also accounting for confounder factors (e.g. birth weight, ...). In case of twins, the analysis will be carried out 1) as mention above, but only including the firstborn and 2) by calculating a mixed model with mother and child as random factor. In case of too many drop outs, descriptive statistics will be carried out.
 
For Gross Motor function measurements at 12 and 24 months, descriptive statistics will be conducted.

--	--

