11.2 Sample size considerations

Data investigating the incidence of PNAC in our unit showed an incidence of 25 % from 2007-9 (unpublished data). We considered a difference of 15% between the groups (incidence of PNAC: 25% for Intralipid and 10% for SMOFLipid, respectively) as a clinically relevant effect. A sample size estimation based on a χ^2 -test indicated that 200 infants (100/group) are required to detect a difference of 15% between the groups with a power of 80% and a significance level of 0.05. The estimated drop out rate is 22%. Therefore, a sample size of 122 patients per group is planned. For sample size estimation, data were assumed to be independent.

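### The supporting PNAC models and the neurodevelopment comparison adjust for variables that arise after randomisation, so their estimates need not measure the effect of assigning the emulsion; the primary chi-square test is not affected

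*Combined protocol and SAP*

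**What the plan says.** The primary analysis in section 11.6.1 is unadjusted: a chi-square "test will be used for analysis of the primary outcome PNAC". Three further analyses bring in covariates.

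- **Additional PNAC model (11.6.1 and synopsis).** A logistic regression with stepwise selection examines treatment together with "other relevant influence factors (i. e. duration of parenteral nutrition, birth weight, amount of enteral feeds in the first week of life". The synopsis names a different set: "duration of parenteral nutrition, birth weight, necrotizing enterocolitis". Neither place gives entry or stay criteria or says that treatment is kept in the model.
- **Infants withdrawn before week 18 whose outcome can be calculated (11.5).** They are analysed per protocol and "by intention to treat analysis, with the duration of treatment as additional covariable".
- **Bayley scores at 12 and 24 months (11.6.2).** A repeated measures ANOVA compares the groups, "also accounting for confounders (e.g. birth weight, IVH Grade 3/4, cystic periventricular leucomalacia, NEC". Apart from the twin variant, this is the only between-group model for the secondary objective. Stepwise selection is not mentioned here.

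On timing, section 7.1.4 runs the interventional phase from randomisation to the end of PN (mean 44 days, SD 34), and section 8.1.1 gives study drug for as long as PN is needed. Section 8.5.4 records time on PN and the neonatal morbidities at discharge, and enteral feeds over days 0 to 6. Section 7.1.2 allows randomisation during the first 5 days of life.

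**The concern.** Randomisation balances baseline confounders on average. A variable that arises afterwards cannot confound the comparison of assigned groups, but it can be a consequence of assignment. Conditioning on it then removes whatever part of the effect passes through it. If it also shares unmeasured causes with the outcome, such as severity of illness, conditioning creates an association that randomisation had ruled out. Section 5.1.2 itself names long-term PN and necrotizing enterocolitis as risk factors for PNAC, and Table 1 lists IVH and NEC under adverse events.

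At stake is whether the adjusted odds ratio, the result labelled intention to treat in 11.5 and the neurodevelopment comparison answer the trial's question. The adjusted odds ratio could disagree with the chi-square result for reasons unrelated to any benefit or harm of the emulsion. In the PNAC model, stepwise selection adds a separate problem: treatment may be dropped, and p-values and intervals computed after selection are not valid.

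**Working it through.** **1. The plan's own figure.** The inputs are "incidence of PNAC: 25% for Intralipid and 10% for SMOFLipid, respectively" (11.2) and "with a power of 80% and a two-sided significance level of 0.05" (synopsis). With a mean rate of 0.175, n per group = [1.96·√(2·0.175·0.825) + 0.842·√(0.25·0.75 + 0.10·0.90)]² / 0.15² = (1.053 + 0.443)² / 0.0225 = 99.5, so 100. This reproduces "200 infants (100/group) are required to detect a difference of 15% between the groups"; power at 100 per group is 80.2%. The corresponding odds ratio is (0.10/0.90)/(0.25/0.75) = 0.33. No covariate enters this calculation.

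**2. Timing of each covariate.**
- PN or treatment duration: starts at randomisation, so wholly after it.
- NEC and cystic PVL: recorded at discharge and may arise after assignment.
- IVH grade 3/4: recorded at discharge; some may precede randomisation.
- First-week feeds: days 0 to 6 against randomisation up to day 5, so partly before and partly after.
- Birth weight: baseline.

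**3. Full mediation (assumed).** PN duration is gamma with mean 44 and SD 34 days (7.1.4). Assume logit P(PNAC) = −3.0 + 0.035 × days, and that the emulsion shortens PN by 30% and acts in no other way. PNAC is then about 23% against 15%. The crude odds ratio is about 0.62 and the duration-adjusted one about 1.0. If a direct odds ratio of 0.33 is added, crude is 0.23 and adjusted 0.33: attenuated, not erased.

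**4. No true effect (assumed).** PN is 30% shorter, and severity drives both PN duration and PNAC. The adjusted odds ratio is about 1.2 to 1.8, depending on the strength of the severity factor.

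**5. Trials of 200 infants (assumed; 1,500 per row).** M stands for PN duration, BW for birth weight and U for an unmeasured cause. M = g·T + 0.7·U − 0.4·BW + 0.7·e, and logit P = a + b·T + c·M + d·U − 0.3·BW, with a and b set to give the stated rates. The within-arm SD of M is √(0.49 + 0.16 + 0.49) = 1.07, so g = 0.3, 0.5 and 1.0 correspond to about 10, 16 and 32 days on the 34-day SD. Stepwise used 0.05 to enter and to stay, with treatment not forced in.

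| True rates 25% v 10% | c, d | Adjusted OR | Power | Stepwise keeps treatment |
|---|---|---|---|---|
| PN unchanged | 0.8, 0.5 | 0.26 | 85% | 86% |
| PN shorter by about 0.3 SD | 0.8, 0.5 | 0.37 | 63% | 62% |
| Shorter by about 0.5 SD | 1.2, 0 | 0.46 | 41% | 39% |
| Shorter by about 1 SD | 1.2, 0 | 0.83 | 7% | 5% |
| Shorter by about 1 SD, shared cause | 1.5, 0.5 | 1.16 | 5% | 7% |
| Longer by about 0.5 SD | 1.2, 0 | 0.14 | 99% | 99% |

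The chi-square test had 80 to 83% power throughout. In the first row the move from 0.33 to 0.26 is the usual change in an odds ratio when a predictor is added (non-collapsibility), not bias.

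With no total effect (25% in both arms) and c = 1.2, d = 0, the adjusted odds ratio was 0.55 when PN was longer by about 0.5 SD and 1.82 when shorter; the model rejected in 36% and 34% of trials. With PN longer by about 0.5 SD but linked to PNAC only through a shared cause (c = 0, d = 1.0), it gave 0.72 and rejected in 15%. The chi-square test rejected in about 5%.

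**6. Baseline adjustment only.** Treatment plus birth weight gave odds ratios of 0.31 to 0.33 and power of 80 to 84% under the true effect, and 1.00 with 4 to 5% rejection under no effect.

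**The case against.** The best defence is that the trial's conclusion rests on the unadjusted chi-square test. The logistic model is introduced as an addition and asks partly about risk factors, where PN duration and NEC are natural terms. This stands as a limit on reach. It does not rescue the model as an estimate of the treatment effect, which 11.6.1 also asks of it and which nothing labels exploratory.

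Section 11.5 is ambiguous, since a chi-square test takes no covariable; the sentence may describe a variant of the logistic model. It still attaches duration to an analysis called intention to treat. Section 11.4 defers details to an SAP, but the text available settles none of this.

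For the Bayley scores, adjusting for morbidities could reduce bias from selective follow-up: section 7.1.1 expects 22% mortality and 60% follow-up after discharge. That supports keeping such a model as a sensitivity analysis, not as the only comparison.

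A reader might infer that the plan will erase or reverse the emulsion's effect. The documents do not support this. They give no effect of the emulsion on PN duration, section 8.1.2 ties the end of PN to enteral feeding, and the mechanisms in 5.1.4 and 5.1.5 (plant sterols, fatty-acid content, bile flow) do not work through PN duration. A reader might also infer that PNAC prolonging PN would by itself exaggerate the benefit. Simulations of 20 extra PN days after PNAC gave no false positive, and where the odds ratio moved, about half or more of the gap was non-collapsibility.

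**Conclusion.** The point holds for three analyses: the additional PNAC model, the duration-adjusted analysis in 11.5 and the Bayley ANOVA. As written, they need not estimate the effect of assigning the emulsion. The primary test and the 100 per group behind it are untouched.

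Size and direction rest on assumptions. If the emulsion does not change the covariate and no cause is shared, there is no bias; in the simulation even a shared cause did no harm while PN duration was unaffected. An assumed shortening of about 10 to 16 days costs the adjusted model roughly 20 to 40 points of power. Erasing a 25% v 10% effect needed a shift of about 1 SD, which is extreme, and the reversal also needed a shared cause. No size was calculated for the Bayley comparison; there the argument is structural, and it is strongest because no unadjusted or baseline-adjusted model is specified.

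The criticism of stepwise selection applies to the PNAC logistic model only. That treatment may be dropped is an inference from the plan's silence on forcing it in.

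**What to change.** - **11.6.1 and synopsis:** prespecify one logistic model with treatment forced in and baseline covariates only (sex, birth weight, gestational age), without stepwise selection. This also settles the mismatch between NEC and first-week feeds.
- **11.5:** delete treatment duration as a covariable from the intention-to-treat analysis. If shortened observation is a concern, handle it in a labelled sensitivity analysis with the method named in advance.
- **11.6.2:** make the main Bayley comparison adjust for the same baseline covariates. Keep a model that adds IVH, PVL and NEC only as a labelled sensitivity or exploratory analysis.
- **PN duration, feeds and NEC:** describe them by arm, or use them in a labelled exploratory risk-factor model for PNAC.

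The baseline variables are already collected under 8.5.4, so no new data are needed. The cost is revised wording, plus the work of choosing a method if the 11.5 sensitivity analysis is wanted. The downside is that risk-factor questions become exploratory.

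### For twins the plan lists two primary analyses without saying which decides the trial, and the first, a valid firstborn-only chi-square, loses power by dropping every second twin

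*Combined protocol and SAP*

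**What the plan says.** Section 8.2 (and the synopsis) allocates twins as follows: "In case of twins, randomization will be applied to the firstborn; the twin will be assigned to the other treatment group". Every enrolled pair is therefore split between the arms.

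Section 11.2 sizes the trial at 100 evaluable infants per group, based on "incidence of PNAC: 25% for Intralipid and 10% for SMOFLipid, respectively", and adds: "For sample size estimation, data were assumed to be independent".

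Section 11.6.1 (and the synopsis) names a chi-square test for PNAC, with a stepwise logistic regression as an additional analysis. Two analyses are then given for twins. The first is "In case of twins, the analysis will be carried out 1) as mentioned above, but only including the firstborn". The second is done "by calculating a generalized linear model with mother as random factor". No sentence says which of the two is confirmatory.

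Section 11.1 defines a modified intention-to-treat set and a per-protocol set. Section 11.5 asks for both when an infant is withdrawn early and does not rank them. Section 11.4 leaves full detail to a statistical analysis plan, but nothing in the combined document settles the order.

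**The concern.** The sample size counts infants, while the first twin analysis counts one infant per mother. Each complete pair supplies two infants towards the recruitment target and only one towards that test. If that test decides the trial, its power is below the planned figure, although the second-born infants have been treated, followed and measured.

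The order also matters. The two analyses use different infants and different variances, so they can disagree. When neither is named in advance, the choice can be made after both results are known. The comparison then no longer has a single 5% error rate.

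**Working it through.** **Inputs.** PNAC 25% versus 10% (section 11.2); "two-sided significance level of 0.05" (synopsis); 80% power and 100 per group (section 11.2); 1:1 allocation with co-twins in opposite arms (section 8.2). The documents give neither the share of infants in twin pairs, t, nor the within-pair correlation. I assume t = 10% to 40% and show a range of correlations. Pairs are taken as complete. I hold the evaluable number at the stated 200, so that this point stays separate from whether 122 enrolled per group is enough to deliver it.

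**Step 1: the plan's own figure.** Pooled chi-square, no continuity correction, mean rate 0.175:

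n per arm = [1.960 × √(2 × 0.175 × 0.825) + 0.842 × √(0.25 × 0.75 + 0.10 × 0.90)]² / 0.15² = [1.0532 + 0.4434]² / 0.0225 = 99.5, rounded up to 100.

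Power at 100 per arm is 80.2%. The plan's figure is reproduced, provided all 200 infants are analysed and are independent.

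**Step 2: firstborn-only power.** The test drops 200 × t/2 infants and leaves m = 200(1 − t/2)/2 per arm. Power = Φ{[0.15√m − 1.0532] / 0.5268}. For m = 90: (1.4230 − 1.0532)/0.5268 = 0.702, so power is 75.9%.

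| Infants in pairs (assumed) | Dropped | Per arm | Power |
|---|---|---|---|
| 10% | 10 | 95 | 78.1% |
| 20% | 20 | 90 | 75.9% |
| 30% | 30 | 85 | 73.4% |
| 40% | 40 | 80 | 70.8% |

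**Step 3: all infants, with and without the pairing.** This is a simulation with 200 infants, 40,000 trials per setting and each pair split across arms. Each cell gives power (%) at binary within-pair correlation 0 / 0.2 / 0.4. The pair-aware test is a score-type test that subtracts the within-pair covariance. It stands in for a mother-clustered model.

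| Infants in pairs | Firstborn only | All infants, pairing ignored | All infants, pair-aware |
|---|---|---|---|
| 10% | 79.5 / 79.1 / 79.5 | 81.8 / 81.9 / 82.2 | 81.6 / 82.1 / 83.0 |
| 20% | 76.9 / 77.0 / 76.8 | 81.3 / 82.0 / 82.5 | 81.0 / 82.6 / 84.3 |
| 30% | 74.5 / 74.4 / 74.4 | 81.6 / 82.3 / 83.4 | 81.3 / 83.5 / 86.1 |
| 40% | 72.0 / 72.2 / 72.0 | 81.4 / 82.8 / 83.5 | 80.9 / 84.5 / 87.3 |

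Simulated power runs about one point above the formula, so gains should be read within this table. A latent (normal-scale) correlation of 0.6 corresponds to a binary correlation of about 0.33 at rates of 25% and 10%. Over latent correlations of 0 to 0.6 the pair-aware power is therefore about 81-86%, and the 87.3% lies just beyond that range.

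**Step 4: where the gain comes from.** At a 20% share and correlation 0.2, using all infants adds 82.0 − 77.0 = 5.0 points, and accounting for the pairing adds 82.6 − 82.0 = 0.6. At a 40% share and correlation 0.4 the two steps add 83.5 − 72.0 = 11.5 and 87.3 − 83.5 = 3.8. Retaining the infants is the larger part in both cases.

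**Step 5: error rates.** With 17.5% PNAC in both arms, type I error is 4.8-5.2% for firstborn-only and 4.9-5.2% for the pair-aware test. If significance on either counts as success, it is 6.0-7.3%, rising with the twin share. Under the planned effect the two tests reach different verdicts in 5% (10% share) to 17% (40% share) of trials.

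**The case against.** The best defence is that the firstborn-only chi-square is simple, needs no modelling assumptions, matches the test used for the sample size and is listed first, so it may be meant as primary. The second analysis already keeps both twins. Details may be settled in a later analysis plan, and twins may be few.

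Much of this stands. Restricting to one infant per mother restores independence, so a reader who infers that this chi-square inflates false positives would be wrong. The independence sentence in section 11.2 concerns the sample size only. A reader might also infer that the plan discards second twins altogether. It does not, because the loss falls on the first analysis alone. Nor does the plan clearly contain a third competing result from a chi-square on all infants. The natural reading is that the firstborn restriction replaces that test when twins are present. Even if it were run, ignoring opposite-arm pairing makes it conservative (3.3-4.7% at correlation 0.4), not too liberal.

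The defence does not supply a ranking. Being numbered first is not the same as being named confirmatory. If it were so intended, the power loss would fall directly on the deciding test. The sizes do depend on the unstated twin share. Early deaths, which the plan treats as drop-outs, would also break some pairs and trim the part of the gain that comes from pairing.

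**Conclusion.** The point holds as a missing ranking together with an avoidable loss of power. It does not show bias or an invalid test. That the ranking is missing is certain from the text. The size of the loss is conditional.

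At 200 evaluable infants, firstborn-only power is about 78% to 71% by formula for an assumed twin share of 10% to 40%. Compared within the simulation, a pair-aware analysis of all infants gains 2-3 points at a 10% share and about 9-14 points at 40% (72% against 81-86%), over latent correlations of 0 to 0.6. The 6-7% type I error applies only if either result were allowed to count. The documents do not say that this is intended, but they do not exclude it. The change is worth making because it is cheap and uses infants already enrolled.

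**What to change.** In section 11.6.1 and the synopsis, name one confirmatory analysis of PNAC on all infants in the modified intention-to-treat set that accounts for mother. One suitable choice is a logistic GEE with mother as the cluster and terms for treatment, sex and birth-weight stratum (below 750 g or not). State that it estimates a marginal odds ratio. A random-mother logistic model estimates a different, mother-specific odds ratio, so the two should not be offered as interchangeable.

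Label the firstborn-only chi-square and the random-mother model as sensitivity analyses, and give the family, link and covariates of the latter. Name the modified intention-to-treat set explicitly. Wording such as all randomised infants would conflict with sections 7.1.5, 11.1 and 11.5, which leave out infants whose outcome cannot be calculated.

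The cost is a change of wording, with no new data or procedures. The downside is that the primary test becomes model-based instead of a simple chi-square. The simulation above used a score-type stand-in, so the exact model should be checked for type I error before it is fixed. At least 200 − 40 = 160 mothers would contribute at the twin shares considered, so the number of clusters is not small.
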